CARI Health's long term goal is to develop a minimally-invasive wearable Remote Medication Monitor (RMM) that provides continuous, real-time data on methadone levels in interstitial fluid (ISF). An RMM could be used as a medication adherence monitor and would allow for the physician, counselor, patient, or family member to remotely verify that a physician-prescribed dose has been taken. Such a verification system can allow methadone clinics greater flexibility in the provision of take-home doses and thus retain more patients in opioid treatment programs.

The purpose of this IRB protocol is to evaluate the early safety and feasibility of detecting methadone in the interstitial fluid (ISF) of subjects taking prescribed daily doses of methadone by using a minimally-invasive remote medication monitor (RMM).

We propose the following study aims:

Aim 1: Determine if an RMM can assess the status of taking a prescribed dose of methadone. To complete this aim, the peak and trough concentrations of a witnessed methadone dose will be assessed in ISF collected through the surface of the skin using existing ISF extraction methods and assessed outside the body via differential pulse voltammetry (**DPV**). We hypothesize that the peak and trough blood samples will correlate with the level of methadone in ISF.

Aim 2: Determine if an RMM can continuously assess the status of taking a prescribed dose of methadone over time. To complete this aim, the pharmacokinetic profile of a witnessed methadone dose will be assessed in ISF continuously from the surface of the skin using the RMM for up to 6 hours. We hypothesize that a clinician can recognize a dose taken from the RMM generated measurement of the methadone in the ISF.

C. Background of the Study

Although reported biosensors have been successful in the identification and quantification of several important biomarkers, most of these devices require invasive means to achieve access to blood samples, thus resulting in pain and suffering on behalf of the individual. Furthermore, only a handful of these devices can provide a

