We will conduct a non-randomized, non-blinded, feasibility study at a single center in the United States. The study will include up to 20 subjects of an equal number of male and female adults (ages 18–70) who have a prescription for methadone for chronic pain. In **Aim 1**, we will determine if an RMM can assess the status of taking a prescribed dose of methadone, using biosamples (i.e., ISF, blood) collected from subjects and tested in a laboratory setup. Biosample collections and pharmacokinetic monitoring will take up to 6 consecutive hours. By completing this aim, we will determine if a physician is able to recognize the peak and trough concentrations of a witnessed methadone dose by DPV or LC-MS data using one of the three available ISF extraction methods described later in this protocol (i.e., Samplimy, Kiffik, or Prausnitz). In **Aim 2**, we will determine if an RMM can continuously assess the status of taking a prescribed dose of methadone over time, by inserting the intradermal microneedle sensing elements of the RMM in the subjects’ skin. The electronics for the RMM prototypes will consist of commercially-available benchtop potentiostats like the PalmSens Sensit BT (<https://www.palmsens.com/product/palmsens4/>) or CH Instruments 660D (<https://www.chinstruments.com/>) and will not be in direct contact with the skin. Biosample collections (i.e., ISF, blood) and pharmacokinetic monitoring will occur over a 6 hour period. By completing this aim, we will determine if a physician is able to recognize a pharmacokinetic profile of a witnessed methadone dose via data collected using intradermal microneedle sensing elements worn continuously on the skin. Completion of Aims 1-2 will require two separate visits.

A. Summary of the Research Design for Aims 1-2

Subject Recruitment Strategy: Up to 20 adults ages 18-80 years of age will be recruited to participate in this study. Subjects will be recruited from pain management clinics and primary care physicians providing control of chronic pain with methadone prescriptions. Human subjects research will be performed at Synergy Research Centers (<https://www.synergypainresearch.com>) in San Diego which is a well-established clinical trial company that provides appropriate staff and facilities to conduct this study.

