 - Diet and exercise habits
 - Tobacco, alcohol and other substance use history
 - Previous pregnancy history (if female)
- The CRC will schedule an in-person clinical visit for the subjects if needed. Subjects will be instructed to take their medications as prescribed by their physician (e.g., dose, dosing times). As such, the in-person visits will be scheduled around the subjects usual dosing time. Subjects will also be asked to abstain from alcohol and non-prescribed substances at least 24 hours before their in-person assessment.

- **In-person study visit within 7 days after the initial consent and online assessment is completed:**

- **Physical assessment (up to 30 minutes; Aims 1-2)**

- The in-person assessment may include the following:

1. Limited physical exam:
 - Height and weight measurements
 - Feeling for the pulse
 - Listening to the heart and lungs with a stethoscope
 - Measuring blood pressure using a sphygmomanometer
2. Changes in medications in the past week
3. Use of substances (e.g., opioids, alcohol) in the past week
4. Urine toxicology test to confirm no other substance use

- b. **Prescribed dose of medication (5 minutes; Aims 1-2)**
 - i. Participants will be asked to take their prescribed methadone medication at the study site. Study personnel shall observe that a dose has been taken.
- c. **Blood sample collections (5 minutes each; Aims 1-2)**
 - i. At medication peak and trough, a standard venipuncture blood sample will be collected by a certified clinician. These samples will be used for comparative analysis with the sensor's ISF Methadone Readings and LC-MS assays of the extracted ISF samples.
- d. **Visit 1 ISF samples collected by 1 of 3 potential methods.**
 - 1. ISF is collected from subjects using one or more of three published extraction methods (i.e., Samplimy, Kiffik, or Prausnitz). The subject is asked for a preference of location (dorsal side of right or left upper arm, or alternatively ventral side of right or left forearm) and the clinician applies the appropriately selected method to collect ISF. If more than one of the three ISF collection methods are applied then it will be applied on the same upper arm or forearm areas by the physician at least 10 cm apart. Participants will have the opportunity to decide whether they are willing to have more than one of the extraction methods administered.

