 - a. **Samplimy Method** (microneedle patch and applicator as per (Ribet et al., 2023)): First applied 1 hour prior to dosing and continued every 15-30 minutes until 4 hrs after dosing (total of 5 hours). An applicator will ensure consistent control of the force and speed of attaching the intradermal microneedle and the pressure required for microneedle extraction [17].
 - a. **Prausnitz Extraction Method** (manual microneedle application): As described in our IRB 002 (#20222142) approved and completed study, a minimally invasive microneedle array will be used in conjunction with a standard vacuum pump. Microneedles (without the patch) will be inserted and removed multiple times (~10) to collect about 1 μ l of ISF. This approach has been well tolerated with faint visual evidence of micropores in the skin in previous studies, including ours [18].
 - b. **Kiffik Method:** A certified physician will place the Kiffik device on the participant's preferred arm. ISF collection will start 2 hrs prior to taking the participant prescribed methadone dose and will end prior to dosing with repeat collections after dosing every 2 hrs until 6 hrs of collection time has ended. Thus, a total of 3 samples will be collected from each participant [19].
- e. **Visit 2 ISF samples collected by 1 of 3 potential methods .**
 - i. The steps listed above (section d #1) will be repeated for visit two (Aim 2), however, in addition to having ISF collected from the skin, the subject will also be applied with up to 3 RMM device(s) and continuously wear them for up to 6 hours. This will replicate how other standard of care continuous monitoring devices (e.g. CGMs) are worn (e.g., <https://www.niddk.nih.gov/health-information/diabetes/overview/managing-diabetes/continuous-glucose-monitoring>). The continuously monitored levels will be compared to the ISF extracted levels as well as the peak and trough blood levels as explained in the analysis section of this protocol.
 - f. The RMM device will consist of a microneedle sensor array wired to a benchtop potentiostat like the PalmSens Sensit BT or CHI 660D. Data will be continuously collected using either bluetooth or data cables. Computer programs will be used to record, measure and analyze methadone and its metabolite levels in the collected sample data. The resultant Differential Pulse Voltammograms will be translated into pharmacokinetic data and securely stored for analysis by the lead research staff.

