 - g. Up to 6 hrs after the application is complete, the microneedles will be removed, the insertion area inspected and a sterile bandage covering will be supplied to the area.

- h. Subjects will be monitored before, during, and 15 minutes after the application to report their tolerability, pain, and experience. Their responses will be documented on a secured google drive spreadsheet, which will be encrypted with a password that adheres to secure GCP certified online storage medium requirements.

- **Method of sample preservation**

- a. Blood samples will be centrifuged and plasma will be kept in the refrigerator.
- b. Collected ISF samples using the single hollowed microneedle with absorbent paper devices will be prepared as outlined by Bird Rock Laboratories and [name] (developer of the Samplimy method).
- c. Collected ISF samples will be analyzed at the time of study and frozen after analysis
- d. All samples will be transported to the laboratory within 7 days of collection and stored in the refrigerator.

- **Follow-up call/visit (15 minutes)**

- a. Approximately 2 days after the microneedle application, subjects will be contacted by the CRC via phone. Subjects will be asked to report their tolerability, pain, and experience. Their responses will be documented in a secure online storage medium.

- **Compensation:**

- a. **Day 1 (Aim 1):** Subjects participating in the first part of this study will be compensated with an online visa gift card worth up to \$250 for their participation. Subjects will be compensated \$25 for the initial online assessment (up to 15-30 minutes), \$25 for the in-person physical exam (up to 30 minutes), \$130 ISF sample collections (up to 6 hours), \$50 using the standard venipuncture with vacuum tube based blood collection (1 pre and 1 post sample per day), and \$20 for the follow-up call (up to 15 minutes).
- b. **Day 2 (Aim 2):** Subjects participating in the second part of this study will be compensated with an online visa gift card worth up to \$250 for their participation subjects will be compensated \$25 for the online assessment (up to 15-30 minutes), \$25 for the in-person physical exam (up to 30 minutes), \$130 for ISF sample collection, continuous sensor application, and data collection (up to 6 hrs), \$50 using the standard venipuncture with vacuum tube based blood collection (1 pre and 1 post sample per day), and \$20 for the follow-up call (up to 15 minutes).

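### Aim 2 is worded as assessing dose status, but every dose is observed and no dose-free RMM segment is assured, so it can estimate only how often a known, witnessed dose is recognised.

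*Protocol*

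**What the plan says.** The Protocol's study aims give Aim 2 as: "Determine if an RMM can continuously assess the status of taking a prescribed dose of methadone over time". The Study Design section then states the operational question more narrowly: "we will determine if a physician is able to recognize a pharmacokinetic profile of a witnessed methadone dose". The same section describes the study as non-randomized and non-blinded, with up to 20 participants, all prescribed methadone.

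Under Prescribed dose of medication, which applies to both aims: "Study personnel shall observe that a dose has been taken".

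Under Visit 2 ISF samples, the Visit 1 extraction steps are repeated and, in addition, "the subject will also be applied with up to 3 RMM device(s) and continuously wear them for up to 6 hours". Removal is timed from application, not from the dose: "Up to 6 hrs after the application is complete, the microneedles will be removed". The planned comparison is: "The continuously monitored levels will be compared to the ISF extracted levels as well as the peak and trough blood levels".

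The repeated extraction steps do carry pre-dose times. For Kiffik: "ISF collection will start 2 hrs prior to taking the participant prescribed methadone dose and will end prior to dosing". For Samplimy: "First applied 1 hour prior to dosing and continued every 15-30 minutes until 4 hrs after dosing". No times are given for Prausnitz. The Compensation section lists one pre and one post blood sample per day.

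Analysis of Study Results has the physician determine the dose taken from the ISF slope between 2 and 4 h. Optionally, the physician may use an AUC ratio with limits of 0.5 and 1.5 that point to noncompliance, referring to a 24 h curve that may be witnessed or unwitnessed.

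**The concern.** Dose status has two values, taken and not taken. Data from known, witnessed doses inform only the first. If every call is made on a recording known to contain a dose, a perfect score cannot separate an informative sensor from a reader who always gives the same answer. Because the study is non-blinded and no masking of the call is described, that reader is not far-fetched.

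A stretch of RMM recording before the dose would give a within-participant, dose-free reference. Whether one exists depends on when the sensor goes on, and the Protocol does not say. This is data acquisition: no analysis plan can recover a pre-dose trace that was never recorded. The omission also lets start times differ between participants, and it puts at risk the pre-dose end of the planned comparison with blood and extracted ISF.

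**Working it through.** The Protocol gives no precision or sample-size calculation, so there is no stated figure to reproduce.

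**1. Traces by true status.** Up to 20 participants have an observed dose at Visit 2 (Study Design; Prescribed dose of medication). Missed, partial or unwitnessed doses scheduled under the RMM: 0. Non-methadone participants: 0.

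**2. What Aim 2 can estimate.** With all n calls correct, the exact (Clopper-Pearson) 95% lower limit is 0.025^(1/n). For n = 20 this is 0.025^(1/20) = 0.832, so 20/20 gives 83% to 100%. A reader who always says the dose was taken scores 20/20 with certainty. The false-call rate is 0/0 and cannot be estimated. No scheduled trace is truly noncompliant, so the ability of the 0.5 and 1.5 limits to flag noncompliance cannot be tested either.

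**3. What the text says about the start of wear.**
- Visit 2 ISF samples: up to 6 h, with no anchor to the dose.
- Removal step: counted from application.
- Study Procedures: device application is listed after pre-dosing blood and before post-dosing blood, which fits a start on either side of the dose.
- Study Design (Aim 2) and Compensation (Day 2): sampling and monitoring share one 6 h block.

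A full 6 h of wear from dosing would give a session of 2 + 6 = 8 h with the Kiffik lead, or 1 + 6 = 7 h with the Samplimy lead. Both exceed 6 h, which favours a pre-dose start. But 6 h is a maximum: wear from dosing for 6 − 2 = 4 h (Kiffik) or 6 − 1 = 5 h (Samplimy) would also fit. The start therefore remains open.

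**4. Comparators without a concurrent RMM reading if wear starts at dosing.**
- Blood: 1 pre and 1 post, so 1 of 2 (taking the trough to be the pre-dose draw).
- Kiffik: 3 samples over 6 h, the first ending before the dose (−2 to 0, 0 to 2, 2 to 4 h), so 1 of 3.
- Samplimy, −1 h to +4 h: every 30 min gives 11 time points, 2 of them pre-dose; every 15 min gives 21, 4 of them pre-dose.

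**5. What a pre-dose start would give.** Two hours before plus 4 h after equals 6 h, matches the Kiffik window and still covers the 2 to 4 h slope. A 3 h lead would leave 3 h after the dose and would not. With one pre-dose segment per participant, 0/20 false calls gives an exact 95% upper limit of 1 − 0.025^(1/20) = 0.168, or 17%. The always-taken reader would show 20/20 false calls (83% to 100%).

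**6. What it costs the 24 h curve.** Extrapolated share of clock time: (24 − 6)/24 = 75% with 6 h of post-dose wear, and (24 − 4)/24 = 83% with 4 h.

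**The case against.** The strongest reply is that the Protocol already narrows the aim. The hypothesis concerns recognising a dose taken, the Study Design section speaks of a witnessed dose, and the study is an early safety and feasibility study that claims no specificity. That stands. What remains is the wider wording of the aim and noncompliance limits that have no matching data.

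A reader might infer that every RMM trace begins after the dose, so that no pre-dose RMM data will exist. The documents do not support this. The shared 6 h block makes a pre-dose start plausible, most clearly under Kiffik, and comparing RMM levels with trough blood implies a pre-dose reading if the trough is the pre-dose draw. The start is unstated; it is not stated to be late. The losses in step 4 are therefore conditional, and the version with a full 6 h of wear from dosing would itself run past the 6 h session.

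It can also be said that masking and segment rules belong in a statistical analysis plan or reader manual. That is fair for the detail, and its absence from the Protocol is not the fault raised here. The start of wear is different, because it decides what is recorded.

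Finally, a pre-dose segment is not a missed dose. This is correct: it is taken at trough, it always comes from a younger sensor than the post-dose segment, and it cannot give specificity for a missed or partial dose. It can still expose an uninformative reader, which the present design cannot do.

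**Conclusion.** The point holds in a limited form. As written, Aim 2 can estimate how often a known, witnessed dose is recognised, at best 20/20 with an exact 95% CI of 83% to 100%. It cannot show that the RMM tells a dose taken from one not taken, and it cannot test the noncompliance limits. A pre-dose RMM reading is plausible but not assured. If wear does start at dosing, 1 of 2 blood samples, 1 of 3 Kiffik samples and 2 of 11 to 4 of 21 Samplimy samples lack a concurrent reading.

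This assumes the maximum of 20 participants, one call per participant, and a trough drawn before the dose. It does not make the feasibility study invalid, because the narrower operational question can be answered. The change is worth making before Visit 2 data are collected, since it is cheap and cannot be made afterwards.

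**What to change.** 1. State under Visit 2 ISF samples that RMM wear begins before the participant's usual dose time, within the existing 6 h and with no change to dosing. One option is to align it with the Kiffik window, 2 h before to 4 h after.
2. Have the study physician read one pre-dose and one post-dose segment of equal length from one pre-named RMM per participant, with time and identity masked and order shuffled. Report correct calls for each type with exact intervals. If a sensor settling period is excluded, shorten both segments equally. Label the pre-dose result a false-call rate on dose-free trough segments, not specificity for a missed dose, because segment type is confounded with sensor age. The reading details may sit in the statistical analysis plan.
3. Limit the Aim 2 conclusion, and any use of the noncompliance limits, to feasibility of recognising a witnessed dose.

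Cost: Protocol wording and some analyst time, with no added visit and no dose withheld. Post-dose wear falls from at most 6 h to about 4 h, so the extrapolated part of the 24 h curve rises from 75% to 83% of clock time. The AUC share depends on the curve shape, which is not given. A 2 h lead adds no time to a Kiffik visit but starts a Samplimy visit about 1 h earlier. For Prausnitz the effect cannot be judged, because no times are stated.

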- c. All subjects will also be provided with 2 meals, snacks, and non-alcoholic beverages during their stay at the study site.

There will be no paper data stored in locked filing cabinets or offices. A unique subject ID code will be created in analytic databases and be used to link all data in an individual file because such linkage is critical for communication with the subject. Research data will be separated from identifying data. All data will be stored on secure password protection servers. Data from this study will be transferred from the secure online service electronically, and stored on secure servers. The research sites used in this study have well established systems for protection of confidential subject information. All computers and files containing confidential information will be password protected and monitored by study staff. As such, the data will be limited to a small number of project investigators and research staff. Backups of electronic data stored in a secure cloud-based location will be maintained at all times.

B. Analysis of Study Results

All the biological samples collected in this study (e.g., ISF (1 ul), blood (2ml), will be tested for methadone and its **r** metabolites at a laboratory that has experience with these types of samples. Urine will be tested for illicit substances to inform eligibility on site with urine drug testing strips.

Concentrations of methadone and its metabolites (EDDP, EMDP, and methadol) will be measured in the

collected ISF, and blood samples using liquid chromatography-tandem mass spectrometry (LC-MS/MS). The study will analyze the data using noncompartmental pharmacokinetic analysis to determine the pharmacokinetic parameters of methadone in the ISF and blood.

Published protocols will be followed for quantitation of methadone and its metabolites.

Determination of the dose taken will be accomplished by the physician using the 2-4hr slope of change in concentration of methadone in the ISF after a witnessed stable dose. The physician may also use the ratio of the area under the ISF dose curve (AUC) for a witnessed individual stable methadone dose divided by the individuals sensed and extrapolated 24hr witnessed/unwitnessed ISF dose curve AUC. (A ratio close to 1.0 confirms compliance to a full dose taken, less than .5 or greater than 1.5 suggests noncompliance. See Rostami et al Poster reference)

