ISF samples collected using the Samplimy or Kiffik method will be assessed using the RMM in the same way that they will be assessed in vivo but with modifications as outlined in the phenylalanine dose taken example study.

Concentration determinations from analyte peaks in the Voltammograms will be correlated to the trough and peak blood methadone levels.

All samples will be safely stored and processed according to Good Clinical Practice Guidelines. None of them will be used for any DNA analysis.

C. Monitoring

N/A

D. Storage of Data

The original electronically signed consent forms will be stored in a secure password protected file online via the Adobe Sign BA agreement based Storage Service. Only the research team members (Principal Investigators/Co-Investigators) and the CRCs will have access to identifiable private information.

An electronic data sheet casebook using GCP certified software will be used for each subject enrolled in the study. The appropriate data sheet will be completed online by the CRCs after each visit. All data collected for the study will be reviewed for quality assurance, data entry, and statistical analysis. All electronic forms will be reviewed for completeness; evident recording errors will be rectified by contact with the appropriate clinical staff. All data sheets will be reviewed by a research team member before final data entry submission. Laboratory Data will be entered within two (2) weeks of a receipt from the independent laboratory. Any corrections will be made electronically.

All biological samples will be stored and processed through standard IRB approved procedures. Subjects will consent to allow their deidentified biological samples to be stored for future use.

All team members will be GCP certified and trained to protect identifiable private information (e.g., signed consent). Deidentified research data will be kept separate from identifiable data in secure GCP certified online locations for the duration of the study. This protocol was designed and will be conducted, recorded, and reported in compliance with the principles of GCP regulations. These requirements are stated in global regulations as well as "Guidance for Good Clinical Practice," International Conference on Harmonization (ICH), and the most recent guidelines of the Declaration of Helsinki of Technical Requirements for Registration of Pharmaceuticals for Human Use.

E. Confidentiality of Data

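### The 2-4 h ISF slope named for dose-taken may be unavailable for a Kiffik-only participant at visit 1, and two blood draws per visit cannot give noncompartmental parameters in blood

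*Protocol*

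**What the plan says.** **Dose-taken.** Section B (Analysis of Study Results) says the determination will be made "by the physician using the 2-4hr slope of change in concentration of methadone in the ISF after a witnessed stable dose". It adds an AUC ratio that the physician may use as well. Neither is tied to a particular extraction method.

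**ISF collection, visit 1 (Study Procedures, item d).** Kiffik collection starts 2 h before the dose and stops before dosing, with "repeat collections after dosing every 2 hrs until 6 hrs of collection time has ended". The item concludes: "Thus, a total of 3 samples will be collected from each participant". Samplimy runs from 1 h before to 4 h after the dose, every 15 to 30 minutes.

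**Number of methods.** The design paragraph speaks of "using one of the three available ISF extraction methods described later in this protocol". Item d says "ISF is collected from subjects using one or more of three published extraction methods", and lets participants decide whether to accept more than one.

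**Visit 2 (item e).** The ISF steps are repeated, and up to 3 RMM devices are worn for up to 6 h.

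**Blood (item c).** "At medication peak and trough, a standard venipuncture blood sample will be collected by a certified clinician". The Compensation section fixes this at one draw before and one after the dose per visit. Section B then promises a noncompartmental analysis giving the pharmacokinetic parameters of methadone in both ISF and blood.

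**The concern.** Recognising a taken dose is the purpose of both aims. Section B names one statistic for it as the stated method, and the AUC ratio is only an option. That statistic needs at least two concentrations at different times inside 2-4 h. The Kiffik schedule may supply one. For a participant sampled only by Kiffik at visit 1, the physician would then have to substitute something the protocol does not define, and the result would not be on the same footing as a Samplimy slope.

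The blood sentence has the same kind of problem: it promises an analysis that the fixed number of draws cannot feed. A later analysis plan can list parameters, but it cannot create samples that the protocol does not collect.

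**Working it through.** **1. Reproduce the Kiffik count.** Inputs from item d: start at -2 h, one collection every 2 h, 6 h of collection in all, 3 samples stated.
- Counting the 6 h from the start: 6 / 2 = 3 collections, at -2 to 0, 0 to 2 and 2 to 4 h. This matches the stated 3.
- Counting 6 h after the dose: 1 + 6/2 = 4. This does not match.

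**2. Readings inside 2-4 h, both ends included.**
- Samplimy every 30 min: (240 - 120)/30 + 1 = 5. Every 15 min: (240 - 120)/15 + 1 = 9.
- Kiffik pooled: 1, an average over the whole window.
- Kiffik spot, taken at the end of each interval: 2, at 2 h and 4 h.

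**3. What slope that allows.**
- *Pooled.* No slope exists within the window. The only post-dose slope joins averages centred at 1 h and 3 h, which is a different quantity. As an illustration only, take an assumed one-compartment steady-state curve (half-life 24 h, once-daily dosing, absorption rate 0.5 to 2.5 per h). The true 2-4 h slope then runs from +0.067 to -0.050 relative units per h, and the slope between the two pooled averages from +0.154 to +0.045. The protocol gives no such inputs, and the finding does not depend on them.
- *Spot.* A slope exists, with residual degrees of freedom 2 - 2 = 0, against 5 - 2 = 3 and 9 - 2 = 7 for Samplimy. Assume a straight line and the same independent error s per reading. The standard error of the slope is then s/√Sxx, where Sxx is the sum of squared distances from 3 h:
  - 2 points: Sxx = 1² + 1² = 2, giving 0.71s per h.
  - 5 points: Sxx = 2(1² + 0.5²) = 2.5, giving 0.63s per h.
  - 9 points: Sxx = 2(1² + 0.75² + 0.5² + 0.25²) = 3.75, giving 0.52s per h.

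  On this reading the loss of precision is modest. What is lost is any way to judge error or curvature from the participant's own data.

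**4. Who is exposed.** One method per participant is allowed, and the split between methods is not fixed. With up to 20 participants, the number with Kiffik alone at visit 1 can be anything from 0 to 20. No RMM is worn at that visit.

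**5. Blood.** There are two draws per visit, one of them post-dose.
- Time of peak: with one post-dose draw it is the scheduled time, not an observed one.
- Peak concentration: nominal, because nothing on either side confirms it.
- Terminal slope: needs several points after the peak, and there are none.
- AUC over the dosing interval: nothing is observed after the post-dose draw. The most available is a one-segment trapezoid up to that draw.

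**The case against.** - **Section B asks for a physician's reading of a slope, not a fitted regression, and spot values at 2 h and 4 h would fall exactly on its ends.** This stands. A reader might infer that Kiffik flatly contradicts the slope rule, but the documents do not support that, because item d never says whether samples are pooled or spot. Pooled is likelier, since the item speaks of collection that starts, ends and accumulates to 6 h, but it is not certain.
- **Section B might seem to force the same statistic on Kiffik,** since samples "collected using the Samplimy or Kiffik method will be assessed using the RMM in the same way that they will be assessed in vivo". That sentence goes on to allow modifications from an example study that is not at hand, and it reads as describing the assay. It is not relied on here.
- **The manual microneedle method has no collection times here.** A reader might count that as a second misfit. The protocol describes that method by reference to an earlier completed study, so the times may be set there. No finding is made.
- **Other routes to dose-taken remain.** This is true. The optional AUC ratio, the peak and trough comparison, and the visit 2 RMM are all untouched. The ratio is not a full substitute for Kiffik, whose ISF stops at 4 h while the ratio relies on extrapolation to 24 h.
- **Blood was drawn for comparison with ISF, and two draws serve that.** This also stands. A reader might infer that the blood sampling is inadequate altogether. It is not: the planned correlation with trough and peak levels is feasible. Only the promise of noncompartmental parameters in blood fails.
- **Simulation could suggest how well a Kiffik contrast separates taken from missed doses.** The protocol gives no pharmacokinetic inputs, and the dose at each visit is witnessed, so there are no missed-dose data to test it on. No such claim is made.

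**Conclusion.** The point holds in two limited parts, both resting on sample counts that the protocol fixes.

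First, the stated dose-taken statistic does not exist for pooled Kiffik samples, and is a two-point line without residual information for spot samples. This matters where Kiffik is the only ISF method at visit 1, for an unfixed number of participants between 0 and 20. It assumes the layout that reproduces the stated count of 3. It does not show that Kiffik cannot reveal a taken dose, or that Aim 1 fails.

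Second, noncompartmental parameters in blood cannot be delivered from one pre-dose and one post-dose draw. What can be delivered is an observed trough and a nominal peak.

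In a feasibility study this should be corrected before analysis. It does not call the design into question.

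**What to change.** **In item d (Kiffik):** state whether each sample is pooled over its interval or a spot value, and record actual start and end times.

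**In section B, dose-taken:** limit the 2-4 h slope to methods with several readings in that window (Samplimy, RMM). For Kiffik, use the change from the pre-dose collection to the 2-4 h collection, or from pre-dose to 4 h if samples are spot values. Report it as a value, without a cut-off. Leave the optional ISF AUC ratio as it stands.

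**In section B, blood:** replace noncompartmental parameters with the observed trough, the observed post-dose (nominal peak) concentration and their ratio, with actual draw times. Keep noncompartmental analysis for ISF.

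**Cost:** rewording in section B and one timing line in item d. No new samples, draws or participants are needed. The downsides are fewer blood parameters and a Kiffik contrast that rests on two values and may be small. For scale only, an assumed one-compartment steady-state model was run with half-life 15 to 60 h, absorption rate 0.3 to 2 per h and ISF delay 0 to 2 h. The lowest pooled contrast after a taken dose ranged from +13.0% (once daily, no delay) to -2.4% (8-hourly, 2 h delay). That is a reason to report the value and not its sign.
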